Recruitment: Participants are recruited by a team that is experienced in conducting transgender research, using a multi-pronged approach including recontacting potentially eligible participants from prior studies who gave permission for future contact; street, agency, and event-based outreach; posting and distribution of Recruitment Flyers; internet-based advertising on Facebook and Grynder.

Additionally, we are collaborating with the CTSI Consultation Service to provide cohort identification and direct mail for recruitment. The Dear Patient letter (attached) will be sent to UCSF patients identified from the APeX record systems via a data extraction by Academic Research Systems (ARS) of patients with a diagnosis of [XXX]. These patients [are/are not] known to or under the care of the researcher team. The CTSI Consultation Service will coordinate the mailing on behalf of the study. Interested subjects will contact the study staff as described in the letter. The data extract will be delivered to the CTSI Consultation Service's MyResearch account in order to facilitate the direct mail activities while ensuring privacy and confidentiality of the patients identified. Protected data elements included in the data pull and delivered to the honest broker may include MRN, name, mailing address, and diagnosis or encounter date. Additional non-PHI data elements may also be collected to facilitate the mailing.

Pre-Screening: Potential participants are pre-screened by Research Assistants (RA) by telephone or in-person at the Alliance Health Project (AHP) site. RAs describe basic study eligibility criteria (>18 years of age, gender, in a relationship, English speaking). For those who provisionally qualify, Partner 1 is pre-screened using a Screening Form in REDCap that includes questions on recent HIV risk, and the name and contact information of the partner. Study RA contacts Partner 2 within one week to pre-screen using a REDCap Screening Form. If the couple is provisionally eligible AND both partners wish to enroll, they are scheduled for an Eligibility Visit at AHP to verify HIV status. If HIV-positive, they are asked to bring documentation of their status.

Eligibility Visit:

1. Visits occur at the AHP site. Both partners attend the Eligibility Visit together at AHP, and RAs conduct Oral Informed Consent with each partner in separate rooms.
2. RA completes an Eligibility Visit Form in REDCap for each partner, and confidentially verifies HIV status by:

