 - a. Review recent (last 30 days) HIV Letter of Diagnosis, HIV medication bottles, or medication prescription;
 - b. Confirm prior participation in the Healthy Divas Study for HIV positive trans women;
 - c. Conduct basic HIV pre-test counseling, OraQuick point-of-care HIV antibody test with saliva

*

from participants' mouth, and disclose result along with post-test counseling .

3. Enter HIV status of the partners in REDCap, which is programmed to inform the RA if the couple may enroll in the study based on their HIV status and responses to eligibility questions. If a potential participant indicates that study participation may pose safety risks to them, a 'flag' is generated in REDCap, and the RAs tell the couple that they are not eligible for the study at this time, but may rescreen in 6 months either together or with a new partner should they break up.
4. Study enrollment requires the participation of both partners, as a couple. If both agree, schedule Enrollment Visit at AHP or remotely. The Enrollment visit can immediately follow the eligibility Visit.
5. RA provides each partner with a visit incentive, Resource List, condoms, and lubricant.

***** If a potential participant has a **new** positive HIV-antibody test result at the Eligibility Visit, the RA provides supportive counseling and provides a Referral List to clinics where HIV confirmatory testing can be obtained. They offer to help set up that appointment and/or accompany them. Care is taken to ensure there is no disclosure to the other partner and the couple is told that they are not eligible for the study at this time, but may rescreen in 6 months either together, or with a new partner should they break up.

Enrollment Visit:

1. Visits occur at the AHP site or remotely. RAs obtain signed Informed Consent from both partners.
2. RAs obtain signed Release of Information Forms to contact HIV medical provider for positive participants, should they be needed for future lab results.
3. RAs collect contact locator information from each partner.
4. For HIV positive participants, a trained phlebotomist draws 20 ml venous blood for viral load testing or the participant is asked to have blood drawn at a Quest Laboratory Service Center.
5. For HIV negative participants who have taken HIV pre-exposure prophylaxis (PrEP) medication in the last 3 months, dried blood spot (DBS) fingerstick procedures are conducted by the phlebotomist or a hair sample is collected for remotely conducted visits.

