Our Data Safety Monitoring Board (DSMB) reviewed and approved this request on February 14, 2022, and our NIMH sponsor approved the request on July 26, 2022.

11.4 * PARTICIPANT AGE RANGE: Eligible age ranges: (REQUIRED)

- 0-6 years
- 7-12 years
- 13-17 years
- 18-64 years
- 65+

11.5 * STUDY POPULATIONS: Data will be collected from or about the following types of people (check all that apply): (REQUIRED)

- Inpatients
- Outpatients
- Family members or caregivers
- Providers
- People who have a condition but who are not being seen as patients
- Healthy volunteers
- Students
- Staff of UCSF or affiliated institutions
- None of the above

11.6 * SPECIAL SUBJECT GROUPS: Check the populations that may be enrolled: (REQUIRED)

- Children / Minors
- Adult subjects unable to consent for themselves
- Adult subjects unable to consent for themselves (emergency setting)
- Subjects with diminished capacity to consent
- Subjects unable to read, speak or understand English
- Pregnant women
- Fetuses
- Neonates
- Prisoners
- Economically or educationally disadvantaged persons
- None of the above

11.7 INCLUSION CRITERIA: Briefly describe the population(s) that will be involved in this study. Include anyone that data will be collected from or about (e.g. patients, healthy controls, caregivers, providers, administrators, students, parents, family members, etc.):

Inclusion criteria:

1. Age 18 or older;
2. Self-reported primary partnership for at least 3 months;
3. Have had sex with primary partner in the last 6 months;
4. Either partner has had condomless sex with any partner in last 6 months;
5. At least one partner must be a trans woman;
6. Able to provide informed consent;
7. English speaking; and
8. Couples may be HIV-negative concordant, HIV-positive concordant, or HIV serodiscordant.

11.8 EXCLUSION CRITERIA: List any exclusion criteria (e.g. reasons why someone would not be included in the study):

Exclusion criteria:

1. Appears to be psychotic, or otherwise unable to complete Informed Consent procedures.
2. Participation would be unsafe.

11.9 * RESEARCH CONDUCTED ON PATIENT CARE WARDS: Do any study activities take place on any patient care units including inpatient wards, peri- or post-operative care units, operating rooms, or in the Emergency Department at UCSF Health medical facilities: (REQUIRED)

Yes No

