*** Did all the participants of previous studies provide permission to be contacted for future studies: (REQUIRED)**

Yes No

12.3 * SEARCHING OF MEDICAL RECORDS: (REQUIRED)

Whose patients are they:

Investigators' own patients or patients seen within the same practice
 Patients not under the care of the investigators

How and by whom will records be accessed and searched (check all that apply):

Self-search in APeX or other medical records source
 Self-search using UCSF's Research Cohort Selection Tool
 CTSI Consultation Service Recruitment Services
 UCSF Academic Research Services (ARS)
 University of California Research Exchange (UC ReX)
 Other method (describe below)

12.4 DETERMINATION OF ELIGIBILITY: How, when, and by whom will eligibility for recruitment be determined:

Potential participants call the study recruitment line or come in person to our community site during drop-in hours. Trained Research Assistants (RAs) will describe the basic study eligibility criteria and complete the Partner 1 Screening Form. If Partner 1 is provisionally eligible, Partner 2 information is collected. Partner 2 is screened within one week by the RAs, using the Partner 2 Screening Form. Both forms are in REDCap, which will inform the RAs if the couple can be scheduled for an Eligibility Visit. At the Eligibility Visit, oral informed consent to be screened is obtained, a brief eligibility survey is administered, and HIV status is verified.

12.5 * INITIATION OF CONTACT: Who initiates contact (check all that apply): (REQUIRED)

Investigators/study team
 UCSF recruitment unit (e.g. CTSI Consultation Services)
 Potential participant
 Other (explain below)

12.6 * HOW IS CONTACT INITIATED: (check all that apply): (REQUIRED)

In person
 Phone
 Letter / email
 Website or app
 Other (explain below)

Attach the telephone recruitment script in the Other Study Documents section of the Initial Review Submission Packet Form. If potential participants will initiate contact, attach the telephone screening script that will be used to provide more information about the study and determine if callers are eligible to participate.

12.7 RECRUITMENT PLAN: Based on the checkboxes you chose above, please provide a narrative describing your recruitment plan. We want to know:

- Who is conducting the search for potential participants, and how?
- How are potential subjects being approached for recruitment? By whom, and when?

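### The Eligibility Visit writes out one distinctive refusal message for only two events, a new positive HIV test and a safety flag, so deductive disclosure to the other partner is not prevented

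*Combined protocol and SAP*

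**What the plan says.** All of this is in the combined protocol and SAP.

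- **Section 8.9, Pre-Screening.** Both partners are screened first. "If the couple is provisionally eligible AND both partners wish to enroll, they are scheduled for an Eligibility Visit at AHP to verify HIV status".
- **Section 8.9, Eligibility Visit.** Partners attend together, consent in separate rooms and have their HIV status verified confidentially. Status is then entered in the REDCap database, "which is programmed to inform the RA if the couple may enroll in the study based on their HIV status and responses to eligibility questions".
- **Section 8.9, Eligibility Visit, item 3 (safety flag).** If a participant indicates that taking part may be unsafe, REDCap raises a flag. The instruction is then: "the RAs tell the couple that they are not eligible for the study at this time, but may rescreen in 6 months either together". Rescreening with someone else after a break-up is also offered.
- **Section 8.9, Eligibility Visit, note on a new positive test.** The research assistant gives supportive counselling and a referral list and offers help with an appointment. "Care is taken to ensure there is no disclosure to the other partner and the couple is told that they are not eligible" for now, followed by almost the same 6-month offer.
- **Section 11.7, criterion 8.** "Couples may be HIV-negative concordant, HIV-positive concordant, or HIV serodiscordant". Section 11.8 lists unsafe participation as an exclusion but not a new positive test.
- **Section 12.4.** At the same visit, "oral informed consent to be screened is obtained, a brief eligibility survey is administered, and HIV status is verified".
- **Section 8.9, Remote Eligibility Visit.** The REDCap decision is repeated. Neither the safety-flag rule nor the new-positive note is.

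**The concern.** The note on a new positive test sets an aim, that the other partner should not learn the result, and in the same sentence a procedure that serves it only weakly. A refusal message conceals its reason only if it is also given for ordinary reasons. Here the 6-month message is written for two reasons, both sensitive and both personal to one partner. It also mentions a break-up.

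The documents recognise what is at stake. Section 8.4 reports that many trans women fear rejection and power differentials when HIV is discussed with a partner. Sections 14.1 and 15.1 name release of confidential information as a risk, and Section 16.3 notes that HIV status could be revealed. For the safety flag, the person at risk is the one who said that participation might be unsafe. Section 8.9 assesses intimate partner violence only in the baseline survey, which a couple turned away at this visit never reaches.

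**Working it through.** No arithmetic applies, because the plan states no figure on this point. The check sets the passages side by side and asks what one partner could conclude.

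1. **Events for which the message is written.** Two: the safety flag (item 3) and a new positive test (the note). The safety-flag wording ends "may rescreen in 6 months either together or with a new partner should they break up", and the note differs from that phrase only by a comma. No other event has a written message.

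2. **Other routes to refusal.** They exist. REDCap also uses answers to eligibility questions (8.9, item 3), a brief eligibility survey is given at the visit (12.4), failed consent comprehension leads to exclusion (12.10), and apparent psychosis or inability to complete consent is an exclusion (11.8). What couples refused on these grounds are told is not stated.

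3. **Ordinary reasons left by the time of the visit.** Few. The couple has already been found provisionally eligible. Several criteria in 11.7, such as relationship length and sex with each other, are facts that both partners share and know. Because all serostatus combinations are admitted, no listed serostatus rule explains a refusal.

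4. **Inference open to a partner who tested negative and raised no safety concern.**
   - If the message is used only for the two written events, the cause is one of two things, both concerning the other person. The partner cannot tell which.
   - If it is also used for other refusals, more causes are possible and the inference is weaker.
   - The documents do not say which case applies.

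5. **Delivery.** Separate rooms are specified for consent (8.9), and separate assessment and testing in 16.4. No section requires the refusal to be given separately. The text says only that the couple is told, which permits joint delivery without requiring it.

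6. **Scope of the protection.** The no-disclosure statement belongs to the new-positive note alone. Sections 14.1 and 15.1 promise that assessment responses are confidential, which arguably reaches the safety answer, but item 3 itself gives no such instruction.

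7. **Consistency of the criteria.** A new positive test defers the couple under 8.9, yet 11.7 admits couples of any serostatus and 11.8 does not list the deferral.

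8. **Size.** A count would need the number of couples reaching the Eligibility Visit, the rate of new positive tests and the rate of safety flags. None is given. The target of 54 couples in Section 8.3 counts randomised couples, not couples screened.

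**The case against.** The strongest reply is that the plan already intends confidentiality and that the gap is one of silence. Much of this stands, and it rules out several stronger readings.

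- **A reader might infer that the message is used only for these two events.** The documents show only that it is written for these two. Other refusals occur, and their couples may hear the same words.
- **A reader might infer that partners are told together.** Joint delivery is not stated. Telling each partner separately would fit the text, and the instruction to avoid disclosure favours that reading.
- **A reader might infer that the other partner can work out the diagnosis.** Sharing one message across two unrelated events gives some masking, so at most the cause is narrowed. The inference also depends on what partners know. The pre-screening briefing in 8.9 covers age, gender, being in a relationship and speaking English. Nothing shown says that couples are told every serostatus combination is admitted, and the recruitment and consent materials are not available here.
- **A reader might infer that the plan promises to conceal the safety flag.** The explicit promise covers only the HIV result.

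What the reply does not remove is that the wording for the two most sensitive refusals is distinctive, has no ordinary reason written alongside it, and comes with no rule on separate delivery. Masking works only if harmless reasons share the message, and the plan does not ensure that they do.

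**Conclusion.** The point holds as a gap in the written procedure that should be closed. Section 8.9 does not prevent deductive disclosure of a new positive HIV result, although it states that aim, and it gives a safety-flagged participant no equivalent protection. The documents do not support calling this a demonstrated breach or a certain disclosure: a partner may suspect that the reason lies with the other person, and no more than that follows.

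The conclusion rests on two readings of silence: that no neutral wording exists for other refusals, and that no instruction elsewhere requires separate delivery. If study materials outside these documents supply both, the remaining work is to bring them into 8.9. The number of couples affected cannot be derived, and the conclusion does not depend on it. There is no bearing on sample size, power or the primary analysis.

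**What to change.** In Section 8.9, Eligibility Visit, item 3 and the note on a new positive test:

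- Have each partner told the outcome separately, in the rooms already used for consent.
- Use one fixed, neutral wording for every couple not enrolled, whatever the reason, with no mention of 6 months, a new partner or a break-up.
- Give any rescreening offer to each person privately.
- State in item 3 that the safety answer is not to be disclosed to the other partner.
- Write the same procedure into the Remote Eligibility Visit text.
- Reconcile the new-positive deferral in 8.9 with the criteria in 11.7 and 11.8, so that the sections agree.

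The cost is a short amendment and retraining on the wording, with no new rooms. Some speculation will remain possible: partners can compare notes, and the extra counselling after a new positive test may be noticed, especially as enrolment can otherwise follow the same day. Giving every couple its decision at a fixed later time would reduce that cue but would give up same-day enrolment. It is optional and not part of this recommendation.

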5. Theory-based mechanisms of action. Covariates will include sociodemographic variables such as age, education and income level, employment, race/ethnicity, living situation, which have been previously found to be structural drivers of HIV risk. While the intervention does not target mental health or substance use, we will assess depressive symptoms using the Center for Epidemiologic Studies Depression Scale (CES-D), and anxiety symptoms will be measured with the Beck Anxiety Inventory. We will also assess alcohol use and other drugs with the AUDIT as well as the Alcohol, Smoking, and Substance Involvement Test (ASSIST) given their associations with HIV outcomes. We will also assess history/current health care engagement (i.e., HIV prevention, primary care, mental health).

Attach any unpublished instruments in the 'Other Study Documents' section of the Initial Review Submission Packet form after completing the study application. Published instruments should NOT be attached.

8.12 * BIOSPECIMEN COLLECTION: Are you drawing any blood or collecting other biosamples (e.g. tissue, buccal swabs, urine, saliva, hair, etc.) for analysis under this protocol and/or storage for future research: (REQUIRED)

Yes No

* Could this study generate genetic data that may be broadly shared (e.g., submitted to NIH in compliance with **Genomic Data Sharing (GDS)/Genome-Wide Association Studies (GWAS)** requirements): (REQUIRED)

Yes No

Please check the Resource Sharing Plan section of your funding notice. You will not be able to share the data as required by your

funding agency if the consent form doesn't include the required language.

8.13 STATISTICAL METHODS: Briefly summarize the methods and types of analyses that will be performed:

Preliminary analyses and missing data. Frequency tables for all variables and measures of central tendency and variability for continuous variables will characterize the sample and will be stratified by study arm to check for imbalances. If the intervention and control groups differ significantly at baseline on one or more covariates, we will use methods based on the Rubin causal model (e.g., propensity scores, double-robust estimation) to obtain the desired marginal effect estimates under the counterfactual assumption of balanced groups.⁸¹⁻⁸⁵ We will address incomplete data with multiple imputation (MI)⁸⁶ because MI makes the relatively mild assumption that incomplete data arise from a conditionally missing-at-random (MAR) mechanism.⁸⁷

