Auxiliary variables will be included to help meet the MAR assumption;^{88, 89} sensitivity analyses will be conducted with weighted MI to assess the MAR assumption's robustness⁹⁰ using SAS⁹¹ and Mplus.

Primary analyses to address Primary Specific Aim 1. If the CHIP intervention is successful, a lower proportion of intervention participants will engage in CR-HIV relative to control group participants following intervention exposure. Therefore, to address Specific Aim 1 we hypothesize that the odds of CR-HIV will be lower for CHIP participants than for control participants (Hypothesis 1). Our primary interest is to estimate the marginal or population-average effects of CHIP exposure on CR-HIV rather than the effect for a hypothetical average subject or couple.⁹² Moreover, within-subject and within-couple CR-HIV correlations are nuisance parameters rather than quantities of interest to be modeled explicitly. Finally, the statistical literature indicates the superior performance of generalized estimating equations (GEE) relative to generalized linear mixed models (GLMMs) for the analysis of dyadic data with categorical outcomes such as CR-HIV.⁹³ Accordingly, we will use GEE for the proposed primary analysis to test Hypothesis 1 by a planned time-averaged comparison of post-baseline measurements of CR-HIV from the intervention group with the post-baseline measures of CRHIV from the control group. Alpha (α) will be set at .05 for this planned comparison. Any additional post-hoc comparisons (e.g., paired comparisons of groups at each time point) will maintain nominal alpha of .05 through the use of simulation-based stepdown multiple comparison methods.⁹⁴ The alternating logistic regression (ALR) approach implemented in SAS PROC GENMOD will be used to address the 3-level clustering of observations within participants and participants within dyads. Though GEE estimates are consistent even if the correlation structure is misspecified, GEE's statistical efficiency improves as the working correlation structure more closely approximates the actual correlation structure;⁹⁵ therefore, various correlation structures suitable for the study's design will be considered (e.g., exchangeable; nested-1).⁹⁶ The QIC statistic will be used to select the final correlation structure.⁹⁷ Couple serostatus will be included as a covariate as required by the stratified randomized design.⁹⁸ Additional relevant covariates such as relationship length, as well as intersectionality criteria and structural drivers (e.g., age, race/ethnicity, poverty, unemployment) will be included if they improve QIC. We will use Robust Huber-White "sandwich" standard errors to obtain correct inferences even if the chosen correlation structure remains slightly misspecified.

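### The stated target is a marginal effect on CR-HIV, but the planned logistic GEE conditions on serostatus and QIC-selected covariates, and no step averages over them

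*Combined protocol and SAP*

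**What the plan says.** Section 8.13 (Statistical methods) describes the target in two places. The paragraph on the primary analyses states: "Our primary interest is to estimate the marginal or population-average effects of CHIP exposure on CR-HIV". It contrasts this with a subject- or couple-specific effect. Under preliminary analyses and missing data, propensity-score or double-robust methods are to be used if the arms differ significantly at baseline, "to obtain the desired marginal effect estimates under the counterfactual assumption of balanced groups".

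The main route is a logistic model: "The alternating logistic regression (ALR) approach implemented in SAS PROC GENMOD will be used" to handle the three-level clustering. On covariates: "Couple serostatus will be included as a covariate as required by the stratified randomized design". Relationship length, age, race/ethnicity, poverty, unemployment and similar variables "will be included if they improve QIC".

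Hypothesis 1 is worded in terms of odds and is tested by a "planned time-averaged comparison of post-baseline measurements of CR-HIV from the intervention group" with the same measurements from control. "Alpha (α) will be set at .05 for this planned comparison". Section 8.13 does not say which number will be reported as the effect, and it contains no step that averages the adjusted model over the covariates.

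**The concern.** An odds ratio is not collapsible. Suppose the arm OR is the same within every covariate pattern, differs from 1, and the covariates predict the outcome. The OR computed from population-averaged risks is then closer to 1, even with perfectly balanced arms. Replacing a random-effects model with GEE removes the conditioning on couple and participant effects. It does not remove the conditioning on serostatus or on whatever QIC admits.

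Prognostic covariates are likely here. Section 8.11 codes CR-HIV through condomless sex with a serodiscordant or status-unknown partner, PrEP adherence and viral suppression. In a concordant couple the primary partner cannot be the serodiscordant one, so risk should vary with couple serostatus. The same section calls the sociodemographic covariates structural drivers of HIV risk.

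What is at stake is the size and meaning of the reported effect. A reader would take the OR as the population effect of offering the intervention. It could not be set directly against the unadjusted ORs and proportion differences of section 11.3, or against an analysis with another covariate set. If the baseline-imbalance branch is triggered, the stated aim is a marginal effect. A chance imbalance could therefore change which quantity is reported.

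**Working it through.** **1. The plan's own effect sizes are on the unadjusted scale.** Inputs from section 11.3: 160 participants after attrition, design effect 1.07, power 0.80, alpha 0.05, four follow-ups, base rate P0 from 0.10 to 0.50, within-subject correlation ρ from 0.20 to 0.80. Sidedness is not stated; two-sided is assumed.

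- ESS = 160/1.07 = 149.5 (stated 149), so 74.5 per arm.
- Effective n per arm = 74.5 / [(1+3ρ)/4], which is 186.25 at ρ=0.2 and 87.6 at ρ=0.8.
- Solve |ln OR| = (1.960+0.842) × √{2/[n·p̄(1−p̄)]}, where p̄ is the mean of the two risks.

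| | Recomputed | Stated (original 100-couple design) |
|---|---|---|
| OR | 0.166-0.556 | 0.17-0.56 |
| Difference | 6.6%-20.4% | 6.6%-20.5% |
| h | 0.275-0.419 | 0.27-0.42 |

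The figures reproduce to rounding with no covariate in the formula, so they are marginal quantities.

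**2. Serostatus alone, by hand.** The stratum shares and risks are assumptions, since the documents give none. Take shares 0.5/0.2/0.3, control risks 0.2/0.3/0.5 and an OR of 0.50 in each stratum.

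- Intervention risks: 0.111/0.176/0.333.
- Mean control risk: 0.5×0.2 + 0.2×0.3 + 0.3×0.5 = 0.310.
- Mean intervention risk: 0.5×0.111 + 0.2×0.176 + 0.3×0.333 = 0.191.
- Marginal OR = (0.191/0.809)/(0.310/0.690) = 0.525.

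With control risks 0.30/0.05/0.60 the means are 0.340 and 0.222, and the marginal OR is 0.554.

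**3. All covariates together.** Let the covariates' contribution to the log-odds be normal with standard deviation s (an assumption), and let Z be standard normal. Choose a so that the mean of expit(a + sZ) equals P0. Set P1 to the mean of expit(a + ln 0.50 + sZ). The marginal OR is [P1/(1−P1)]/[P0/(1−P0)].

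| s | P0=0.10 | P0=0.30 | P0=0.50 |
|---|---|---|---|
| 0.25 | 0.502 | 0.504 | 0.505 |
| 0.5 | 0.506 | 0.515 | 0.519 |
| 1 | 0.527 | 0.553 | 0.563 |
| 1.5 | 0.562 | 0.599 | 0.612 |

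On the log scale, at s=1 and P0=0.50, ln 0.50/ln 0.563 = 0.693/0.575 = 1.21, a 21% difference; at P0=0.10 it is 8%. For s up to 0.5 it is at most about 6%. In risk terms at s=1 and P0=0.50, applying an OR of 0.50 to the overall risk gives 0.333, a fall of 16.7 points. The averaged risk is 0.360, a fall of 14.0 points. If the conditional OR is 1, the marginal OR is also 1.

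**4. Movement with the covariate set.** Large simulated trial of 60,000 couples, true conditional OR 0.50, assumed serostatus shifts of −1 and +1 on the logit scale, and one normal covariate with the slope shown.

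| Slope | Arm only | + serostatus | + serostatus and covariate | Last model standardised |
|---|---|---|---|---|
| 0 | 0.536 | 0.509 | 0.509 | 0.539 |
| 0.5 | 0.547 | 0.523 | 0.506 | 0.550 |
| 1 | 0.572 | 0.553 | 0.494 | 0.574 |

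Within each row the arm OR moves away from 1 as prognostic covariates enter. Standardising the fullest model returns the arm-only value to within simulation error.

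**The case against.** The strongest reply is that the quoted sentence contrasts a marginal effect with one for an average subject or couple, treats the correlations as nuisance parameters and prefers GEE to mixed models. In that sense a covariate-adjusted GEE is population-averaged, and the plan delivers what the sentence asks. This stands: a reader might infer that the primary-analysis paragraph flatly contradicts itself, and it does not. The covariate-marginal reading draws its support from the causal-model wording in the preliminary-analyses paragraph, so the same term is used where two quantities are possible.

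Second, the plan specifies a test and never names the arm coefficient as the reported estimate. That also stands. Reporting it is an inference from a hypothesis worded in odds with no other summary given.

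Third, a reader might infer that the reported OR will overstate the effect. The documents do not support this as a general statement, because they give no covariate strengths. The gap is negligible for weak covariates and absent under the null. Small-trial simulations can also exaggerate it. With 54 couples and strong assumed covariates, the median adjusted OR was 0.36 against a marginal OR of 0.45. With 300,000 couples the adjusted OR was 0.373, so part of that gap is finite-sample bias.

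Fourth, the imbalance branch lists its methods only as examples and names no OR. It cannot be said to yield a marginal OR for certain; only its stated aim is marginal.

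Finally, section 8.13 is meant as a brief summary, and QIC selection is a prespecification question that standardising does not settle. Both are fair, but neither supplies the missing definition of the effect measure.

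**Conclusion.** The point holds in a limited form. The plan aims at a marginal effect, its main route yields an arm OR conditional on serostatus and on any covariates QIC retains, and nothing averages over them. If that OR is reported as the Hypothesis 1 effect, it is further from 1 than the covariate-marginal OR whenever the effect is non-null and the covariates are prognostic. For an adjusted OR of 0.50, the gap runs from almost nothing to about 0.11 on the OR scale over logit SDs of 0.25 to 1.5. That range rests on assumed covariate strength, a normal prognostic score and a constant conditional OR.

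A reader might infer that the alpha 0.05 test is compromised. It is not: without arm-by-covariate interaction the two nulls coincide, so this issue by itself changes the size and interpretation of the estimate, not the type I error.

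**What to change.** Keep the GEE and the planned alpha 0.05 test. In section 8.13, under the primary analyses, add that the Hypothesis 1 effect estimate is the standardised marginal risk difference and marginal OR, obtained as follows:

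1. From the fitted model, predict CR-HIV risk for every randomised couple at each of the four follow-up visits, once with arm set to intervention and once to control. Use the same unit of analysis as the primary model; section 8.11 defines CR-HIV per couple, while section 8.13 models participants within dyads, so the unit must be stated.
2. Average the predictions within each arm setting, then form the risk difference and OR.
3. Compute couple-clustered standard errors (robust with the delta method, or a bootstrap of couples) and combine them across the multiple imputations.
4. Report the adjusted arm OR as supportive and label it covariate-conditional.

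The cost is modest extra programming and a reported OR that may be slightly less favourable. No new data are needed.
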